6.2 DEFINITION OF DOSE-LIMITING TOXICITIES

DLTs will be evaluated during the safety lead-in (dose de-escalation phase) of the trial. The period for evaluating DLTs will be from the time of first administration of study drug until 6 weeks (1.5 cycles). Any treatment-related toxicities that first occurred during the DLT period must be followed for resolution to determine if the event qualifies as a DLT as specified in the DLT criteria below. Patients who do not remain on the study up to this time for reasons other than DLT will be replaced with another patient at the same dose level. Grading of DLTs will follow the guidelines provided in the Common Terminology Criteria for Adverse Events (CTCAE) version 5.0.

To be considered a DLT, an AE must be at least possibly related to the investigational product or regimen and meet the criteria listed below. Toxicity that is clearly and directly related to the primary disease or to another etiology is excluded from this definition. The DLT criteria are specified in the following lists.

Hematologic toxicity:

- Grade ≥ 3 neutropenia complicated by fever $>38.3^{\circ}\text{C}$
- Grade ≥ 3 neutropenia that does not improve \leq Grade 1 within 7 days
- Grade 4 neutropenia (lasting more than 7 days)
- Grade ≥ 3 thrombocytopenia with significant bleeding
- Grade 3 thrombocytopenia that is not associated with clinically significant bleeding and does not improve by at least 1 grade within 7 days
- Grade 4 thrombocytopenia (regardless of duration)
- Grade 4 anemia (regardless of duration)

Non-hematologic toxicity:

- Any Grade 4 non-immune-mediated AE
- Any Grade 4 immune-mediated AE, excluding endocrinopathies
- Any Grade 3 non-immune mediated AE, including fatigue, that does not resolve to \leq Grade 1 or baseline within 30 days with optimal medical management
- Any Grade 3 immune-mediated AE – excluding diarrhea/colitis, pneumonitis, hepatitis, rash, neurotoxicity, myocarditis, myositis/polymyositis, endocrinopathies and nephritis – that does not resolve to \leq Grade 2 or baseline within 15 days and to \leq Grade 1 within 30 days after onset of the event, despite optimal medical management including systemic corticosteroids

- Grade 3 diarrhea or colitis
- Grade 3 noninfectious pneumonitis
- Grade 2 noninfectious pneumonitis that does not resolve to \leq Grade 1 within 3 days of the initiation of maximal supportive care
- **Aspartate aminotransferase (AST) or alanine aminotransferase (ALT) $\geq 3 \times$ ULN** with concurrent increase in total bilirubin (TBL) $\geq 2 \times$ ULN without evidence of cholestasis or alternative explanations (e.g., viral hepatitis, disease progression in the liver; i.e., “Hy’s Law”)
- ALT or AST $> 8 \times$ ULN or TBL $> 5 \times$ ULN
- Grade 3 immune-mediated rash that does not resolve to \leq Grade 1 or baseline within 30 days
- Grade 2 rash covering $> 30\%$ BSA that does not resolve to \leq Grade 1 or baseline within 30 days
- Any grade of immune-mediated rash with bullous formation
- Grade 3 immune-mediated neurotoxicity (excluding Guillain-Barre and myasthenia gravis) that does not resolve to \leq Grade 1 within 30 days
- Grade 2 or 3 immune-mediated peripheral neuromotor syndrome (such as Guillain-Barre and myasthenia gravis) that does not resolve to \leq Grade 1 within 30 days or that exhibits signs of respiratory insufficiency or autonomic instability
- Grade 3 immune-mediated myocarditis
- Any symptomatic immune-mediated myocarditis that does not become asymptomatic within 3 days of initiating optimal medical management including systemic corticosteroids
- Grade 2 or 3 immune-mediated myositis/polymyositis that does not resolve to Grade ≤ 1 within 30 days of initiating optimal medical management including systemic corticosteroids or that exhibits signs of respiratory insufficiency regardless of optimal medical management
- Immune-mediated increase in creatinine $> 3 \times$ ULN, or $> 3 \times$ baseline for patients with a baseline creatinine elevated above ULN

The DLT definition excludes the conditions listed below.

- Grade 3 endocrine disorder (thyroid, pituitary, and/or adrenal insufficiency) that is managed with or without systemic corticosteroid therapy and/or hormone replacement therapy and the patient is asymptomatic
- Grade 3 inflammatory reaction attributed to a local antitumor response (e.g., inflammatory reaction at sites of metastatic disease, lymph nodes, etc.)
- Concurrent vitiligo or alopecia of any AE grade
- Grade 3 infusion-related reaction (first occurrence and in the absence of steroid prophylaxis) that resolves within 6 hours with appropriate clinical management
- Grade 3 or 4 lymphopenia
- Isolated Grade 3 electrolyte abnormalities that are not associated with clinical signs or symptoms and are reversed with appropriate maximal medical intervention within 14 days

In the absence of a clinically significant abnormality, repeat laboratory testing will be conducted to confirm significant laboratory findings prior to designation as a DLT.

6.3 TOXICITY MANAGEMENT GUIDELINES

It is possible only one of the investigational agents is deemed attributed to causality of an AE, in this instance, only the attributed study drug may be held. Per principal investigator discretion, the treating investigator may elect to hold the study drug they deem attributable to the experienced AE.

6.3.1 DURVALUMAB

Guidelines for the management of immune-mediated reactions, infusion-related reactions, and non-immune-mediated reactions for durvalumab are provided in the durvalumab Toxicity Management Guidelines (TMGs). Please see **Section 6.3** and **Appendix A**.

Patients should be thoroughly evaluated and appropriate efforts should be made to rule out neoplastic, infectious, metabolic, toxin, or other etiologic causes of the irAE. Serologic, immunologic, and histologic (biopsy) data, as appropriate, should be used to support an irAE diagnosis. In the absence of a clear alternative etiology, events should be considered potentially immune related.

In addition, there are certain circumstances in which durvalumab should be permanently discontinued (**Appendix A**). Following the first dose of investigational product, subsequent administration of durvalumab and AVB-S6-500 can be modified based on toxicities observed. These guidelines have been prepared to assist the Investigator in the exercise of his/her clinical judgment in treating these types of toxicities. These guidelines apply to AEs considered causally related to durvalumab monotherapy and the durvalumab + AVB-S6-500 regimen by the reporting investigator

Following determination of RP2D, **dose reductions are not permitted**.

Patients should be thoroughly evaluated and appropriate efforts should be made to rule out neoplastic, infectious, metabolic, toxin, or other etiologic causes of the irAE. Serologic, immunologic, and histologic (biopsy) data, as appropriate, should be used to support an irAE diagnosis. In the absence of a clear alternative etiology, events should be considered potentially immune related.

All toxicities will be graded according to NCI CTCAE, Version 5.0.

6.3.2 AVB-S6-500

The safety, pharmacokinetic and pharmacodynamic profile of AVB-S6-500 has been evaluated in healthy volunteers in a single-ascending dose (SAD) and repeat-dose (RD) Phase 1 clinical study (AVB500-HV-001). AVB-S6-500 was well tolerated at all doses evaluated in healthy volunteers.

Following the establishment of RP2D, **dose reductions are not permitted**. In addition, there are certain circumstances in which AVB-S6-500 should be permanently discontinued (see **Appendix A**).

6.3.3 COMBINATION TREATMENT REGIMEN

In addition to the individual toxicity management guidelines for durvalumab and AVB-S6-500 described above management of any potential overlapping toxicities that may occur following treatment with this combination must be considered. For AEs that are considered at least partly due to administration of durvalumab or AVB-S6-500, treat each of the toxicities with maximum supportive care (including holding the agent suspected of causing the toxicity where required). If the symptoms promptly resolve with supportive care, consideration should be given to continuing the same dose of durvalumab or AVB-S6-500 along with appropriate continuing supportive care.

For these subjects, once the AE resolves to permit resumption of the investigational combination, if the AE recurs at a dose-limiting severity, AVB-S6-500 and durvalumab dosing should be held until the recurrence until the AE resolves to Grade 1 or baseline. The AE should resolve to Grade 1 or baseline within 21 days for the subject to be considered for continued treatment. If the AE does not resolve to Grade 1 or baseline within 21 days, the investigator should consult the MDACC IND Office to determine feasibility of continued treatment with AVB-S6-500 and durvalumab.

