Appendix A. Dosing Modifications and Toxicity Management Guidelines for Durvalumab and AVB-S6-500

Table 16. General Considerations regarding Immune-Mediated Reactions

These guidelines are provided as a recommendation to support investigators in the management of potential immune-mediated adverse events (imAEs).

Immune-mediated events can occur in nearly any organ or tissue; therefore, these guidelines may not include all the possible immune-mediated reactions. Investigators are advised to take into consideration the appropriate practice guidelines and other society guidelines (e.g., NCCN, ESMO) in the management of these events. Refer to the section of the table titled “Other - Immune-Mediated Reactions” for general guidance on imAEs not noted in the “Specific Immune-Mediated Reactions” section. Early identification and management of immune-mediated adverse events (imAEs) are essential to ensure safe use of the study drug. Monitor patients closely for symptoms and signs that may be clinical manifestations of underlying immune-mediated adverse events. Patients with suspected imAEs should be thoroughly evaluated to rule out any alternative etiologies (e.g., disease progression, concomitant medications, infections). In the absence of a clear alternative etiology, all such events should be managed as if they were immune-mediated. Institute medical management promptly, including specialty consultation as appropriate. In general, withhold study drug/study regimen for severe (Grade 3) imAEs. Permanently discontinue study drug/study regimen for life-threatening (Grade 4) imAEs, recurrent severe (Grade 3) imAEs that require systemic immunosuppressive treatment, or an inability to reduce corticosteroid dose to 10 mg or less of prednisone or equivalent per day within 12 weeks of initiating corticosteroids.

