		
 – Acetaminophen and/or antihistamines may be administered per institutional standard at the discretion of the investigator. – Consider premedication per institutional standard prior to subsequent doses.
	For Grade 2 The infusion rate of study drug/study regimen may be decreased 50% or temporarily interrupted until resolution of the event. Subsequent infusions may be given at 50% of the initial infusion rate.	
 – Steroids should not be used for routine premedication of Grade ≤ 2 infusion reactions.
Grade 3 or 4	For Grade 3 or 4 Permanently discontinue study drug/study regimen.	For Grade 3 or 4
		
 – Manage severe infusion-related reactions per institutional standards (e.g., IM epinephrine, followed by IV diphenhydramine and famotidine, and IV glucocorticoid).
		CTCAE Common Terminology Criteria for Adverse Events; IM intramuscular; IV intravenous; NCI National Cancer Institute.

Table 20. Non-immune-mediated Reactions

Severity Grade of the Event (Refer to NCI CTCAE applicable version in study protocol for defining the CTC grade/severity)	Dose Modifications	Toxicity Management
Any Grade	Note: Dose modifications are not required for AEs not deemed to be related to study treatment (i.e., events due to underlying disease) or for laboratory abnormalities not deemed to be clinically significant.	Treat accordingly, as per institutional standard.
Grade 1	No dose modifications.	Treat accordingly, as per institutional standard.
Grade 2	Hold study drug/study regimen until resolution to \leq Grade 1 or baseline.	Treat accordingly, as per institutional standard.
Grade 3	Hold study drug/study regimen until resolution to \leq Grade 1 or baseline. For AEs that downgrade to \leq Grade 2 within 7 days or resolve to \leq Grade 1 or baseline within 14 days, resume study drug/study regimen administration. Otherwise, discontinue study drug/study regimen.	Treat accordingly, as per institutional standard.
Grade 4	Discontinue study drug/study regimen (Note: For Grade 4 labs, decision to discontinue should be based on accompanying clinical signs/symptoms, the Investigator's clinical judgment, and consultation with the MDACC IND Office and supporting companies.).	Treat accordingly, as per institutional standard.

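### Section 6.3.3 and Appendix A give different stopping rules for certain AEs that recur at dose-limiting severity, and no passage says which governs

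*Combined protocol and SAP*

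**What the plan says.** **Section 6.3.3 (combination regimen).** The section opens "In addition to the individual toxicity management guidelines for durvalumab and AVB-S6-500 described above", so it presents itself as an addition to those guidelines. For a patient who has resumed treatment after an AE, "if the AE recurs at a dose-limiting severity, AVB-S6-500 and durvalumab dosing should be held". The recovery condition is "The AE should resolve to Grade 1 or baseline within 21 days for the subject to be considered for continued treatment". If it is not met, "the investigator should consult the MDACC IND Office to determine feasibility of continued treatment with AVB-S6-500 and durvalumab". Nothing in the section excepts a grade or a type of event.

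**Appendix A, general considerations (Table 16).** "Permanently discontinue study drug/study regimen for life-threatening (Grade 4) imAEs, recurrent severe (Grade 3) imAEs that require systemic immunosuppressive treatment".

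**Appendix A, specific reactions (Table 17).** Grade 3 or 4 pneumonitis and Grade 3 or 4 myocarditis lead to permanent discontinuation with no recovery window. For a patient on a PD-L1 inhibitor, Grade 3 diarrhea/colitis leads to permanent discontinuation unless it reaches Grade 1 or lower within 14 days.

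**Section 4.3.1.** Item 5 ends investigational product for any AE that meets discontinuation criteria in Section 6.3. Item 6 does so for a clinically significant DLT attributable to both drugs.

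**Sections 9.2 and 9.2.1.** The proportion of subjects discontinuing because of AEs (treatment-related AEs in 9.2.1) is to be estimated with a 90% confidence interval.

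**The concern.** A recurrence at dose-limiting severity is a point at which an investigator needs one clear instruction. Section 6.3.3 tells the investigator to hold, wait and, if necessary, ask about continuing. For some of the same events Appendix A says to stop for good. Two investigators, or one investigator with two similar patients, could act differently and both be following the protocol.

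Two things are at stake. The first is patient safety, because the passages differ on whether re-exposure is open for discussion. The second is the meaning of the discontinuation proportion, which would depend partly on which passage was followed.

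**Working it through.** This is a comparison of texts; the plan states no figure to reproduce.

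**Step 1: which recurrences trigger 6.3.3.** The trigger is recurrence at dose-limiting severity, a term the section does not define. The natural reference is the DLT list in Section 6.2, so each case below is tested against it.

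**Step 2: can the situation arise?** Yes. Appendix A allows resumption after Grade 2 pneumonitis, after Grade 2 myocarditis that improves rapidly to Grade 0, and after Grade 3 colitis that recovers in time. Each of these could then recur at Grade 3.

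**Step 3: side by side.** For every row, 6.3.3 says: hold both drugs, allow 21 days to reach Grade 1 or baseline, then consult.

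| Recurrent event | DLT under 6.2? | Appendix A | Where the texts part |
|---|---|---|---|
| Grade 3 noninfectious pneumonitis | Yes | Permanent discontinuation | From onset |
| Grade 3 immune-mediated myocarditis | Yes | Permanent discontinuation | From onset |
| Grade 3 diarrhea/colitis | Yes | Permanent discontinuation if not Grade 1 or lower within 14 days | Days 15 to 21 (21 − 14 = 7 days), and beyond |
| Grade 4 immune-mediated AE, other than endocrinopathy or amylase/lipase elevation | Yes | Permanent discontinuation | From onset |
| Recurrent Grade 3 immune-mediated AE needing systemic immunosuppression | Where the event meets a 6.2 criterion, as colitis does | Permanent discontinuation | From when that treatment is needed |

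The last row matters most for interpretation: "recurrent severe (Grade 3) imAEs that require systemic immunosuppressive treatment" is a rule written for recurrences, so Appendix A cannot be confined to first events.

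**Step 4: cases that do not belong in the table.**
- *Non-immune Grade 3.* Table 20 of Appendix A allows resumption if the AE falls to Grade 2 or lower within 7 days or to Grade 1 or baseline within 14; "Otherwise, discontinue study drug/study regimen". Under 6.2, however, a non-hematologic Grade 3 AE of this kind is a DLT only if unresolved at 30 days. On the strict reading, recovery on days 15 to 21 never triggers 6.3.3. Some hematologic criteria, such as Grade 3 neutropenia not improved within 7 days, still could.
- *Grade 4 exceptions.* Endocrinopathies are outside the DLT definition, and Appendix A does not require stopping for them. For amylase/lipase elevation it allows continuation to be considered. For non-immune Grade 4 laboratory values it relies on judgment and consultation.
- *Other windows.* Grade 3 neuromotor syndromes and myositis have 30 days, and Grade 3 rash has no stated limit.

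**Step 5: does another passage settle it?** Section 4.3.1 item 5 points to Section 6.3. That section contains 6.3.3 itself as well as the references to Appendix A in 6.3.1 and 6.3.2, so the pointer does not rank them. Item 6 adds a third rule, under which a clinically significant DLT attributable to both drugs ends treatment with no recovery window.

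**Step 6: size.** No frequency can be derived. Section 3.1 says that enrollment ended after the fifth evaluable subject completed treatment on the lead-in; step 3 of the dose-finding rules in Section 9 caps the lead-in at 15. Taking these as denominators (an assumption, since the safety set could differ), one patient weighs 1/5 = 20 percentage points or 1/15 = 6.7. The unacceptable-toxicity measure in Section 11.1 already counts any treatment-related AE of Grade 3 or higher, so the events in the table enter it whichever passage is followed.

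**The case against.** The strongest reply is that the texts can be read together. Section 6.3.3 never orders continuation: recovery within 21 days is a necessary condition for being considered, not a sufficient one. It calls itself additional to the individual guidelines, and Section 4.3.1 item 5 stops anyone who meets a discontinuation criterion. On that reading Appendix A stops the patient first and 6.3.3 only adds an outer limit. Appendix A also describes its immune-mediated guidance as a recommendation.

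Part of this stands. It would be wrong to say that 6.3.3 tells the investigator to continue; the accurate statement is that it leaves continuation open. But the harmonized reading has to be supplied by the reader. Consulting on whether treatment can continue does not fit with permanent discontinuation of the same event, and calling Appendix A a recommendation makes precedence less clear.

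A reader might also infer broader conflicts, which the documents do not support:
- *That Appendix A generally stops treatment at 14 days, or that any Grade 4 event must stop.* Step 4 of the working shows other windows and several Grade 4 exceptions.
- *That every recurrent non-immune Grade 3 AE recovering on days 15 to 21 is caught.* Most are not DLTs under 6.2, and the 7-day Grade 2 alternative allows some to resume.
- *That a recurrence always gets more time than a first event.* Where Appendix A gives 30 days, 21 is shorter.
- *That the discontinuation rate is off by 7 to 20 points.* Those figures are one patient's weight in a small denominator, not an estimated effect.

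**Conclusion.** The contradiction holds for the events in the table. For them, Section 6.3.3 leaves continued treatment open while Appendix A calls for permanent discontinuation; Section 4.3.1 does not resolve the difference, and no precedence is stated. This rests on reading *dose-limiting severity* as the Section 6.2 definition. A looser reading would widen the conflict to more non-immune Grade 3 recurrences, which is itself a reason to define the term.

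The consequence is possible inconsistency in patient management and in what counts toward the discontinuation proportion. Its frequency is unknown: it requires an AE, resumption, recurrence at dose-limiting severity, and an outcome on which the passages differ. DLTs are judged by the Section 6.2 criteria, not by whether treatment stopped, so dose-finding, sample size and operating characteristics are unaffected. With enrollment closed, the point matters for any patient still on treatment, for reporting which rule was applied, and for any reuse of the text. It should be corrected.

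**What to change.** Reconcile Sections 4.3.1 (items 5 and 6) and 6.3.3 with Appendix A. Three pieces of wording are needed:
- whether *dose-limiting severity* in 6.3.3 means the Section 6.2 definition;
- which passage governs when 6.3.3, 4.3.1 and Appendix A differ;
- whether the hold-and-consult procedure in 6.3.3 applies to events for which Appendix A calls for permanent discontinuation.

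Which clinical rule should apply, and whether it should be the same for all events, is for the sponsor and investigators to decide. If any patient has already had such a recurrence, the study report should say which rule was followed and how the patient was counted in the discontinuation proportion. The cost is protocol wording only, with no change to the design, sample size or analysis methods.

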6.4 RESTRICTIONS DURING THE STUDY AND CONCOMITANT TREATMENT(S)

6.4.1 SUBJECTS OF CHILD-BEARING POTENTIAL

Female subjects of childbearing potential who are not abstinent and intend to be sexually active with a non-sterilized male partner must use at least 1 **highly** effective method of contraception (**Table 3**) from the time of screening throughout the total duration of the drug treatment and the drug washout period (90 days after the last dose of study drug). Non-sterilized male partners of a female patient of childbearing potential must use a male condom plus spermicide throughout this period. Cessation of birth control after this point should be discussed with a responsible physician. Periodic abstinence, the rhythm method, and the withdrawal method are not acceptable methods of birth control. Female patients should also refrain from breastfeeding throughout this period.

Females of childbearing potential are defined as those who are not surgically sterile (i.e., bilateral salpingectomy, bilateral oophorectomy, or complete hysterectomy) or post-menopausal.

Women will be considered post-menopausal if they have been amenorrheic for 12 months without an alternative medical cause. The following age-specific requirements apply:

- Women <50 years of age would be considered post-menopausal if they have been amenorrheic for 12 months or more following cessation of exogenous hormonal treatments and if they have luteinizing hormone and follicle-stimulating hormone levels in the post-menopausal range for the institution.
- Women ≥50 years of age would be considered post-menopausal if they have been amenorrheic for 12 months or more following cessation of all exogenous hormonal treatments, had radiation-induced menopause with last menses >1 year ago, had chemotherapy-induced menopause with last menses >1 year ago.

Highly effective methods of contraception, defined as one that results in a low failure rate (i.e. less than 1% per year) when used consistently and correctly are described in **Table 3**. Note that some contraception methods are not considered highly effective (e.g. male or female condom with or without spermicide; female cap, diaphragm, or sponge with or without spermicide; non-copper containing intrauterine device; progestogen-only oral hormonal contraceptive pills where inhibition of ovulation is not the primary mode of action [excluding Cerazette/desogestrel which is considered highly effective]; and triphasic combined oral contraceptive pills).

Table 3. Highly Effective Methods of Contraception (<1% Failure Rate)

Barrier/Intrauterine methods	Hormonal Methods

• Copper T intrauterine device• Levonorgestrel-releasing intrauterine system (e.g., Mirena®)^a	
• Implants: Etonogestrel-releasing implants: e.g. Implanon® or Norplant®• Intravaginal: Ethinylestradiol/etonogestrel-releasing intravaginal devices: e.g. NuvaRing®• Injection: Medroxyprogesterone injection: e.g. Depo-Provera®• Combined Pill: Normal and low dose combined oral contraceptive pill• Patch: Norelgestromin/ethinylestradiol-releasing transdermal system: e.g. Ortho Evra®• Minipill: Progesterone based oral contraceptive pill using desogestrel: Cerazette® is currently the only highly effective progesterone-based

^a This is also considered a hormonal method

